6.5.3 Renal function

For each subject, the estimated creatinine clearance values (without 24 hr urine collection) will be calculated using the Cockcroft-Gault and the abbreviated MDRD formulas separately (as specified in Table 6-3). In these calculations, the body weight is the last measurement collected on or before the day when the subject takes the laboratory test and age should also be calculated based on the time when the subject takes the laboratory test.

If the creatinine value is collected in the unit $\mu\text{mol/L}$ (SI unit), it will be converted to mg/dL in order to use the formulas. The conversion is via the equation below:

- $\text{mg/dL} = 88.4 \mu\text{mol/L}$ (e.g., creatinine = 2.0 mg/dL = 176.8 $\mu\text{mol/L}$).

Table 6-3 Creatinine clearance calculation

Variable	Formula
Creatinine clearance [mL/min] using Cockcroft-Gault formula (Cockcroft and Gault, 1976)	$= (140 - A) \times W / (72 \times C) \times G$ 
Where
 
A is age [years]
 
W is body weight [kg]
 
C is the serum concentration of creatinine [mg/dL]
 
G is a constant: G=1 for males and G=0.85 for females.

Creatinine clearance [mL/min] using abbreviated MDRD formula (Levey et al, 2000)	$= 186.3 \times C^{-1.154} \times A^{-0.203} \times E \times S$ 
Where
 
C is the serum concentration of creatinine [mg/dL],
 
A is age [years],
 
E is ethnicity: E=1.212 if patient is black, else E=1,
 
S is gender: S=0.742 (if patient is female), else S=1.

The estimated creatinine clearance will be included as one of the laboratory parameters.

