6.5.3 Vital signs

Vital signs will be recorded according to the schedule in [Table 6-1](#), [Table 6-2](#) and [Table 6-3](#). Vital signs will include height, weight, sitting pulse rate, sitting systolic and diastolic blood pressure, and oral temperature (degrees Celsius).

Heart rate (pulse)

Sitting radial pulse after 5 minutes of rest should be measured just prior to blood pressure measurement.

At least 6 hour monitoring in the clinic will be required on Day 1 (Visit 3) and Visit 15 after first dose of study drug in the Core and Extension Phase, respectively. This is also required in the event of an increase in fingolimod dose from 0.25 mg to 0.5 mg (see [Section 3.3](#)) and at any restart of study drug dosing after an interruption as specified in [Section 5.5.5](#). Details of the monitoring during treatment initiation, dose increase or study drug restart are provided in [Appendix 2](#).

In the Extension Phase, Visit 15 first dose monitoring must be done by the independent first dose monitoring team. All subsequent monitoring visits required per protocol for dose increases or study drug interruptions may be performed by the main study team since all patients will be treated with fingolimod in the Extension Phase and thus blinding is not required after the first dose of Extension Phase medication has been provided to a patient.

Blood pressure

Sitting blood pressure will be recorded according to the schedule in [Table 6-1](#), [Table 6-2](#) and [Table 6-3](#). Every effort should be made to have the same study personnel obtaining blood pressure readings for an individual patient at each visit at the same time of day with the same equipment. Using a calibrated standard sphygmomanometer with the appropriate cuff size, arterial blood pressure determinations will be made. With the arm supported at the level of the heart, systolic and diastolic blood pressure will be recorded. The cuff should not be deflated at a rate greater than 2 mmHg/sec.

At each visit after the patient has been resting (i.e., not active) for 5 minutes, systolic/diastolic blood pressure will be measured three times. For blood pressure measurements during first dose monitoring on Day 1, refer to [Appendix 2](#).

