6.5.2 Clinically notable criteria

Clinically notable abnormalities criteria are summarized in Table 6-2.

All applicable post-baseline laboratory results will be checked against the respective notable criteria. For a particular notable criterion, a subject will be counted in the notable abnormal

category as long as one of the results meets the criterion. Note that a subject can be counted in both low and high abnormal categories.

For some laboratory parameters, subjects may have a character value of "<x.x" or "<x" instead of the actual numeric value which is below the lower limit of detection (LLOD). The 50% of the LLOD rule will be applied to transform a character value into a numerical value. This rule will be applied to all applicable laboratory values prior to checking against the notable criteria as well as computation of any statistics.

Table 6-2 Criteria for clinically notable abnormalities

Hematology	Less Than	Greater Than
Hemoglobin	10 g/dL	20 g/dL
Hematocrit	0.3	0.6
RBCs	3,300,000/mm ³	6,800,000/mm ³
WBCs	3000/mm ³	15,000/mm ³
Granulocytes (Poly, neutrophils)	1000 mm ³	12000/mm ³
Lymphocytes	200 mm ³	8000 mm ³
Platelets	100,000/mm ³	600,000/mm ³
Chemistry		
Glucose	70 mg/dL (fasting and random)	120 mg/dL (fasting) 200 mg/dL (random)
Calcium	7.5 mg/dL	11.6 mg/dL
Sodium	130 mEq/L	150 mEq/L
Potassium	3.0 mEq/L	5.2 mEq/L
Chloride	85 mEq/L	119 mEq/L
BUN	2 mg/dL	30 mg/dL
Creatinine	0.2 mg/dL	1.6 mg/dL
eGFR		>19% decrease from baseline
Total bilirubin	0 mg/dL	1.2 mg/dL
SGOT (AST)	0 U/L	100 U/L
SGPT (ALT)	0 U/L	110 U/L
GGT	0 U/L	120 U/L
LDH	0 U/L	500 U/L
Alkaline Phosphatase*		
10 <-13 years	42 U/L (m) / 51U/L (f)	362 U/L (m) / 332 U/L (f)
13 <- 16 years	74U/L (m) / 50 U/L (f)	390 U/L (m) / 162 U/L (f)
16 <-18 years	52 U/L (m) / 47 U/L (f)	171 U/L (m) / 119 U/L (f)
18 years and above	37 U/L (m) / (f)	116 U/L (m) / (f)
Total Protein	4.0 g/dL	9.5 g/dL
Albumin	2.5 g/dL	6.0 g/dL
Uric Acid	1.5 mg/dL	10.0 mg/dL
*Ranges according to NIH Clinical Centre [http://cclinprod.cc.nih.gov/dlm/testguide.nsf ; 10 th May 2012]		
Urinalysis clinically notable values		Abnormality
Parameter		
WBC		>5
RBC		>5
Protein		+ or greater*
Glucose		+ or greater*
* Trace should proceed +, otherwise ++ or greater		

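### The SAP's >19% eGFR flag does not say which of two height-free renal estimates it uses, and in growing patients the two can give opposite answers

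*SAP*

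**What the plan says.** SAP 6.5.3 (Renal function) derives estimated creatinine clearance for each subject: it "will be calculated using the Cockcroft-Gault and the abbreviated MDRD formulas separately". The terms in SAP Table 6-3 are:

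- Cockcroft-Gault: age, weight, creatinine and sex ("G is a constant: G=1 for males and G=0.85 for females").
- Abbreviated MDRD: creatinine, age, ethnicity ("E is ethnicity: E=1.212 if patient is black, else E=1") and sex ("S is gender: S=0.742 (if patient is female), else S=1").

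The inputs move with time: "the body weight is the last measurement collected on or before the day when the subject takes the laboratory test", and age is taken at the test date. SAP 6.5.4 summarizes both estimates.

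SAP Table 6-2 lists eGFR as notable on a ">19% decrease from baseline". It does not define eGFR or tie it to either formula. Under SAP 6.5.2, one qualifying post-baseline result is enough to count a subject.

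Height is available: Protocol 6.5.3 states "Vital signs will include height, weight, sitting pulse rate". SAP 6.8.1 already uses height, with separate equations below 18 years, to predict lung function. Protocol 4.1 admits patients from age 10 up to the 18th birthday, and the core phase lasts up to 24 months.

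**The concern.** Many of these patients grow during follow-up. Weight gain pushes Cockcroft-Gault up whatever the kidneys do. MDRD has nothing to offset a creatinine rise that accompanies growth, and it falls slightly with age alone. The same child can therefore improve on one estimate and decline on the other.

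Because Table 6-2 names neither estimate, a programmer cannot tell from the SAP which one drives the notable count, or whether both do. The choice matters. With MDRD, a modest creatinine rise during growth may be counted as notable. With Cockcroft-Gault, a large creatinine rise may be hidden by weight gain. What is at stake is whether a renal safety table in a paediatric population can be read. Efficacy, type I error and power are not touched.

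**Working it through.** **Check on the plan's own figure.** The one worked number in SAP 6.5.3 is the unit conversion: 2.0 mg/dL × 88.4 = 176.8 µmol/L. It reproduces.

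**Inputs.** The formulas are from SAP Table 6-3. Ages 10 to 17 are from Protocol 4.1. Weights of 25 and 30 kg at the young end are from Protocol 3.3, which puts 25 kg near the 5th percentile at age 10 and expects most patients to weigh at least 30 kg. Other weights, all creatinine values and all heights are assumptions, because the documents give no patient values. The only creatinine bounds are the notable limits of 0.2 and 1.6 mg/dL.

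**Formulas** (A = age, W = weight, C = creatinine in mg/dL):

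- Cockcroft-Gault = (140 − A) × W / (72 × C) × G
- MDRD = 186.3 × C^−1.154 × A^−0.203 × E × S

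Within a patient, G, E and S cancel. With r = C1/C0, the follow-up to baseline ratios are:

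- Cockcroft-Gault: [(140 − A1)/(140 − A0)] × (W1/W0) / r
- MDRD: (A1/A0)^−0.203 × r^−1.154

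The flag fires when the ratio is below 0.81.

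**Growth from age 10 to 12, 30 to 40 kg.** Cockcroft-Gault is (128/130) × (40/30) / r = 1.313/r. MDRD is 1.2^−0.203 × r^−1.154 = 0.964 × r^−1.154.

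| Creatinine ratio r | Cockcroft-Gault | MDRD |
|---|---|---|
| 1.00 | +31.3% | −3.6% |
| 1.10 | +19.3% | −13.7% |
| 1.20 | +9.4% | −21.9% (flag) |
| 1.50 | −12.5% | −39.6% (flag) |
| 1.70 | −22.8% (flag) | −47.8% (flag) |

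The first row holds at any creatinine level. The flag thresholds are:

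- Cockcroft-Gault: r > 1.313/0.81 = 1.62
- MDRD: r > (0.964/0.81)^(1/1.154) = 1.16

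**Growth from age 12 to 14, 42 to 55 kg, creatinine 0.5 to 0.6 (assumed).**

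- Cockcroft-Gault: (126/128) × (55/42) / 1.2 = 1.074, or +7.4%, no flag.
- MDRD: 0.969 × 0.810 = 0.785, or −21.5%, flag.
- Height/creatinine with assumed height 150 to 163 cm: (163/150)/1.2 = 0.906, or −9.4%, no flag.

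If creatinine rises only to 0.55, MDRD is −13.2% and does not flag. Over this growth, the creatinine rise needed to flag is about 17% for MDRD, 34% for height/creatinine (1.087/0.81) and 59% for Cockcroft-Gault.

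**Near-grown patient.** For a boy aged 15 to 17, 55 to 60 kg, 0.7 to 0.8 (assumed), Cockcroft-Gault is −6.1% and MDRD −16.4%. They move the same way and neither flags.

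**Level.** For a boy aged 10, 30 kg, 0.5 mg/dL, Cockcroft-Gault is 130 × 30/36 = 108 and MDRD is 260, a ratio of 2.40. For a girl the values are 92 and 193, a ratio of 2.09. Over 25 to 30 kg, both sexes, creatinine 0.3 to 1.0 and E = 1, the ratio runs from about 1.9 to 3.1. At age 17 and 60 kg it is about 0.9 to 1.2.

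**The case against.** Several points on the other side stand.

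- A reader might infer that the two- to threefold gap in level invalidates the flag. It does not: a constant multiplier cancels in a within-patient percent change. The gap matters only for the by-visit summaries of level.
- A reader might infer that the table is bound to flag normal growth. The documents give no creatinine trajectory, so this cannot be shown. At constant age, a step from 0.5 to 0.6 mg/dL moves MDRD by 1.2^−1.154 − 1 = −18.97%, which does not exceed 19%.
- The most affected patients are few. SAP section 2 expects only a small number at or below 40 kg, and the Amendment 7 rationale describes pre-pubertal patients as scarce.
- Randomization is 1:1 and stratified by puberty status (Protocol 5.2 and 5.3), so growth should affect both arms alike.
- Both estimates are tabulated, so disagreement would be visible. Creatinine and BUN have their own notable limits, and cystatin C is collected (Protocol 6.5.4). The absolute creatinine limit is a weak substitute, however: 1.6 mg/dL is 3.2 times an assumed baseline of 0.5.
- Applying the criterion to both estimates is a natural reading of SAP 6.5.2 and 6.5.3. But it is not stated, and it would leave one child both notable and not notable.
- No renal finding appears in the list of mandatory discontinuation criteria (Protocol 5.5.9).

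These points limit the consequence. They do not supply the missing definition or remove the dependence on growth.

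**Conclusion.** The concern holds in a limited form. As written, the >19% flag is ambiguous and, in growing patients, confounded by growth. Over the same two years from age 10 (30 to 40 kg), the creatinine rise needed to flag is about 16% on one estimate and about 62% on the other. Those two thresholds depend on the assumed growth but not on any creatinine level. The discordant-flag example at ages 12 to 14 does rest on an assumed creatinine rise, and it disappears for MDRD if the rise is 10% instead of 20%.

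To call the flag uninterpretable would go too far. Near-grown patients are little affected, and growth in both arms means false or masked flags rather than a biased treatment comparison. The documents also give no paediatric reference range, so they do not support calling the high MDRD values implausible. They do not describe either formula as intended for adults. The point rests on the absent height term and the undefined flag. It is a cheap improvement to a safety summary.

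**What to change.** 1. In SAP Table 6-2, define eGFR as one estimate proportional to height divided by serum creatinine, and base the >19% decrease on it. Use the height rule already in SAP 6.8.1: the same visit, otherwise the nearest available measurement.
2. Apply that estimate to each patient's baseline and every core-phase visit, even if the patient turns 18 on study. The proportionality constant then cancels. Switching equations at 18 would put baseline and follow-up on different scales and make the percent change depend on the constant. The documents give no constant, so if levels are also tabulated the sponsor must state and reference one.
3. Keep Cockcroft-Gault and MDRD, if wanted, as secondary summaries for comparison with the adult trials, and state that they do not drive the flag.
4. Reconcile the mL/min label on both formulas in SAP Table 6-3 with the ml/min/1.73 m² used for GFR in Protocol 4.2.

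The cost is SAP wording and one extra derived variable, with no new data collection. The downside is a less direct comparison with adult tables, which item 3 partly offsets.

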6.5.4 Data Summaries

All laboratory parameters (excluding all hematology % values except % for white cell differential values) and the estimated creatinine clearance calculated using the Cockcroft-Gault formula and the abbreviated MDRD formula will be summarized.

Summaries on the SAF set by treatment group include:

- Summary statistics and changes from baseline in lab results (hematology and biochemistry) by visit
- Summary statistics of percent of baseline in hematology results by visit
- Incidence of notable laboratory abnormalities (based on criteria in Table 6-2)
- Incidence of notable laboratory abnormalities by visit
- Frequency (%) distributions of liver function test results and hematology results in pre-defined categories (as specified in the table shells); For liver function tests, the frequencies and percentages of subjects with elevations of certain times upper limit normal will be summarized by treatment group.
- Shift table (low, normal, or high as defined by the normal ranges) from baseline to post-baseline extreme values in hematology and biochemistry results

- Shift table (positive and negative) from baseline to post baseline in Urinalysis results.
- Neutralizing antibodies (Nabs) to IFN at Month 24 by treatment

For non by-visit summaries, visits defined by visit-windows will not be used. All available data from scheduled and unscheduled visits will be considered.

Summaries on the follow-up set by treatment group include:

- Frequency (%) distributions of liver function test results and hematology results in pre-defined categories (as defined in the table shell) by time-window (days 1 to 45 after study drug discontinuation and more than 45 days after study drug discontinuation)

Plots on the SAF set by treatment group include:

- Box and whisker plot of liver function tests results by visit
- Line plot of liver function test results for patients meeting liver function notable criteria
- Box and whisker plot of hematology results by visit
- Line plot of hematology results for patients meeting hematology notable criteria

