 - ALT, AST, alkaline phosphatase, GGT, >2 x upper limit of normal (ULN) range for age (for pre-pubertal patients > 1 X ULN or > 2 X ULN if currently treated with IFN or glatiramer acetate). Elevations of alkaline phosphatase should not be used in isolation to exclude subjects, and would require Investigator discretion.
 - Bilirubin elevations not in the context of Gilberts Syndrome: Total and conjugated bilirubin >1.5 X ULN (for pre-pubertal patients >1 X ULN or > 1.5 X ULN if currently treated with IFN or glatiramer acetate).
 16. Patients with severe renal insufficiency (GFR <30 ml/min/1.73 m²).
 17. Patients with lymphocyte count < 800 cells (mm³).
 18. Patients with any of the following neurologic/psychiatric disorder:
 - History of any type of epileptic seizure(s) as well as psychogenic non-epileptic seizure(s) during the past 12 months before screening;
 - History of substance abuse (drug or alcohol) or any other factor (i.e., serious psychiatric condition) that may interfere with the subject's ability to cooperate and comply with the study procedures;
 - Progressive neurological disorder, other than MS, which may affect participation in the study or require the use of medications not allowed by the protocol
 19. Patients unable to undergo MRI scans, including claustrophobia or history of hypersensitivity to gadolinium-DTPA.
 20. Pregnant or nursing females, where pregnancy is defined as the state of a female after conception and until the termination of gestation, confirmed by a positive HCG laboratory test.

21. Female patients of childbearing potential, defined as all females physiologically capable of becoming pregnant, unless they agree to abstinence or, if sexually active, the use of contraception as defined in [Section 6.6](#).
22. History of hypersensitivity to any of the study drugs or to drugs of similar chemical classes.
23. Patients with a score of “yes” on item 4 or 5 of the Suicidal Ideation section of the C-SSRS, if this ideation occurred in the past 6 months, or with a score of “yes” on any item of the Suicidal Behavior section, except for “Non-Suicidal Self Injurious Behavior”, if this behavior occurred in the past 2 years.
24. Patients who have received an investigational drug or therapy within 180 days or 5 half-lives of randomization, whichever is longer.

No additional exclusions may be applied by the investigator, in order to ensure that the study population will be representative of all eligible patients.

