9.5.3 Safety variables

Core Phase:

All safety analyses will be conducted on data from the Safety Analysis set. The assessment of safety will be based mainly on the incidence of adverse events and on the incidence of clinically notable laboratory abnormalities. Other safety assessments will include laboratory data summaries, vital signs, bradycardia events, pulmonary function tests, ophthalmic, and ECG data.

Adverse events will be summarized by presenting, for each treatment group, the number and percentage of patients having any adverse event by primary system organ class and preferred term. Severe AEs, serious AEs, drug related AEs and the AEs leading to premature discontinuation of study drug will be presented in a similar format as adverse events. Notable events will include death, non-fatal SAEs (including infections) and AEs (including infections) leading to discontinuation from the study. The summary will be tabulated by treatment group. The incidence rate (adjusted by treatment duration i.e., incidence rate per 100-patient years) will also be provided for any AE by system organ class and preferred term.

Laboratory data will be summarized by presenting summary statistics of raw data and change from baseline values, by presenting shift tables using clinically notable ranges (baseline to most extreme post-baseline value), and by flagging notable values in data listings. For liver function tests, the frequencies and percentages of patients with elevations of 1, 2, 3, 5, and 8 times upper limit normal will be summarized by visit and treatment group.

The incidence of patients with neutralizing antibodies (Nabs) to IFN at EOS-CP will be summarized by treatment group.

Vital sign data will be summarized by presenting summary statistics for change from baseline values (both for the period 6 hours post first dose and for further assessments). The incidence of post-baseline notable vital sign abnormalities will be summarized. Further, the frequency distribution for pulse by visit and the frequency distribution for percent decline in pulse during first 6 hours will be presented.

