6.4.3 Data summaries

The following summaries will exclude hourly vital sign data from the first dose or second dose or restart dose monitoring (first dose data discussed in Section 6.7.1).

Summaries on the SAF set by treatment group include:

- Summary statistics and changes from baseline in vital sign parameters by visit
- Frequency (%) distributions of highest SBP, DBP, and lowest pulse in pre-defined categories respectively (as specified in the table shell);
- Incidence of notable vital sign abnormalities based on the notable criteria in Table 6-1

Summaries on the FUS by treatment group include:

- Incidence of notable vital sign abnormalities based on the notable criteria in Table 6-1 will be summarized by time-window (days 1 to 45 after study drug discontinuation, and more than 45 days after study drug discontinuation)

Plots on the SAF set by treatment group include:

- Box and whisker plot of vital signs by visit

Table 6-1 Criteria for clinically notable vital signs

Vital Sign	Age group	Notable criteria	
Heart Rate	<12 years	>130 bpm or increase of ≥ 15 bpm from baseline Or	
		<70 bpm or decrease of ≥ 15 bpm from baseline	
	≥ 12 years	>120 bpm or increase of ≥ 15 bpm from baseline Or	
		<50 bpm or decrease of ≥ 15 bpm from baseline	
Systolic Blood Pressure	<12 years	≥ 125 mmHg or increase of ≥ 20 mmHg from baseline Or	
		≤ 70 mmHg or decrease of ≥ 20 mmHg from baseline	
	≥ 12 to <18 years	≥ 160 mmHg or increase of ≥ 20 mmHg from baseline Or	
		≤ 90 mmHg or decrease of ≥ 20 mmHg from baseline	
	≥ 18 years	≥ 180 mmHg or increase of ≥ 20 mmHg from baseline or	
		≤ 90 mmHg or decrease of ≥ 20 mmHg from baseline	
	Diastolic Blood Pressure	<12 years	≥ 85 mmHg or increase of ≥ 15 mmHg from baseline Or
			≤ 50 mmHg or decrease of ≥ 15 mmHg from baseline
≥ 12 to <18 years		≥ 95 mmHg or increase of ≥ 15 mmHg from baseline Or	
		≤ 50 mmHg or decrease of ≥ 15 mmHg from baseline	
≥ 18 years		≥ 105 mmHg or increase of ≥ 15 mmHg from baseline Or	
		≤ 50 mmHg or decrease of ≥ 15 mmHg from baseline	
Temperature		>38.3 °C or an absolute change ≥ 1.1 °C from baseline	

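### The SAP omits the protocol's laboratory shift table by clinically notable range, so no listed hematology or chemistry table separates new from pre-existing notable values

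*SAP*

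**What the plan says.** Protocol 9.5.3 describes the safety assessment as "based mainly on the incidence of adverse events and on the incidence of clinically notable laboratory abnormalities". It says that laboratory data will be summarized, among other ways, "by presenting shift tables using clinically notable ranges (baseline to most extreme post-baseline value), and by flagging notable values in data listings".

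SAP 6.5.2 sets the counting rule: "All applicable post-baseline laboratory results will be checked against the respective notable criteria". It continues: "For a particular notable criterion, a subject will be counted in the notable abnormal" category once any single result meets the limit. Neither sentence refers to the baseline value.

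SAP 6.5.4 lists the outputs. For hematology and biochemistry the only shift table is: "Shift table (low, normal, or high as defined by the normal ranges) from baseline to post-baseline extreme values in hematology and biochemistry results". The same list has incidence of notable abnormalities against Table 6-2, overall and by visit. SAP 3.8.4.2 defines visit windows for post-baseline data only, so the by-visit table has no defined baseline column.

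**The concern.** The normal range and the notable range answer different questions. A normal-range shift table shows who moved outside the laboratory's reference limits. It does not show who crossed a Table 6-2 limit. The incidence table does use Table 6-2, but it mixes patients who crossed a limit on treatment with patients who were beyond it before the first dose. The protocol's shift table is the output that would tell them apart, and the SAP does not list it.

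Notable laboratory incidence is one of the two main supports of the safety assessment. The other support handles the same issue explicitly: under Protocol 7.1 a pre-existing condition is an adverse event only if it worsens, and SAP section 6 excludes adverse events that start before the first dose. No listed table does this for hematology or chemistry. A reader of the study report could not tell how much of a notable-value count arose on treatment.

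**Working it through.** The documents state no figure on this point, so there is none to reproduce. The check has three steps.

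**1. The two plans side by side (hematology and chemistry)**

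| Item | Protocol 9.5.3 | SAP 6.5.2 and 6.5.4 |
|---|---|---|
| Incidence of notable values | Yes, no baseline condition | Yes, no baseline condition |
| Shift, baseline to extreme | By clinically notable range | By normal range |
| Notable baseline against notable post-baseline | Given by the shift table | In no listed table |

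Two outputs are partial exceptions. Table 6-2 defines notable eGFR as a fall of more than 19% from baseline, so it is new by construction. Urinalysis keeps a positive/negative shift table.

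**2. Can an enrolled patient already be notable?**

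- Bilirubin: yes in Gilbert's syndrome. Exclusion 15 reads "Bilirubin elevations not in the context of Gilberts Syndrome: Total and conjugated bilirubin >1.5 X ULN", so it sets no ceiling for Gilbert's patients, while Table 6-2 flags total bilirubin above 1.2 mg/dL. For other patients the answer depends on an upper limit of normal (ULN) that the documents do not give: 1.5 × ULN exceeds 1.2 mg/dL only if ULN is above 1.2 / 1.5 = 0.8 mg/dL. Pre-pubertal patients not on interferon or glatiramer acetate face a stricter 1 × ULN.
- Alkaline phosphatase: yes. Exclusion 15 says that an isolated elevation should not by itself exclude a patient and leaves it to the investigator.
- Glucose, potassium, hemoglobin and platelets: possible, since the exclusion criteria set no numeric limit.
- Low lymphocytes: not expected. Exclusion 17 removes counts below 800/mm3, and the notable limit is below 200/mm3.

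**3. Size, by illustration**

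Let b be the share notable at baseline, assumed equal in both arms and persistent, and i the true new-onset rate among the rest. Neither is in the documents.

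Counted rate = b + (1 − b) × i. Absolute difference = (1 − b) × (i₁ − i₂).

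With i of 10% against 5% (ratio 2.0, difference 5.0 points):

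| b | Counted rates | Ratio | Difference (points) | Share of counted patients not new (b / counted rate) |
|---|---|---|---|---|
| 2% | 11.8% vs 6.9% | 1.71 | 4.9 | 17% vs 29% |
| 5% | 14.5% vs 9.75% | 1.49 | 4.75 | 34% vs 51% |
| 10% | 19.0% vs 14.5% | 1.31 | 4.5 | 53% vs 69% |

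With i of 3% against 1% (ratio 3.0, difference 2.0 points), the counted rates are 4.9% vs 3.0%, 7.9% vs 6.0% and 12.7% vs 10.9%. The ratios are 1.7, 1.3 and 1.2, and the differences 1.96, 1.90 and 1.80 points.

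In patients, at the planned 95 per arm (Protocol 9.6), b = 5% and 10% against 5%: 13.8 and 9.3 patients would be counted, of whom 95 × 0.05 = 4.75 in each arm were notable before treatment.

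**The case against.** **The counting rule follows the protocol.** This stands. Protocol 9.5.3 puts no baseline condition on notable incidence either. Counting every post-baseline notable value is also the inclusive choice: restricting the count to patients not notable at baseline would drop someone who starts just over a limit and then worsens greatly, such as bilirubin going from 1.3 to 5 mg/dL. The gap is the missing companion table, not the count.

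**The SAP does not expressly withdraw the protocol's table.** SAP sections 1 and 2 defer to Protocol section 9, so a reader should not infer a deliberate replacement. But SAP 6.5.4 is the list from which tables will be programmed, it names a different shift table, and the Amendment 2 change entry does not mention the difference. Silence leaves the two documents unreconciled.

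**Other outputs carry baseline information.** Partly true. Change from baseline, percent of baseline, line plots for patients meeting liver or hematology notable criteria, and listings are all planned. They work at group level or patient by patient, and none cross-tabulates notable status. The category tables depend on shells that are not in the documents, so a baseline row there cannot be ruled out.

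**Stronger readings that a reader might infer.**

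- *Drug-induced lymphopenia would be hidden.* It would not. Given the entry limit of 800/mm3, the incidence table for low lymphocytes already shows new onset.
- *The safety comparison is biased.* Randomization balances baseline carriage on average, and the absolute difference barely moves.
- *Chance imbalance in carriage would swamp a real effect.* Its SD, √(2b(1 − b)/95), is 2.0, 3.2 and 4.4 points at the three assumed shares. Those shares are not in the documents. Even with new onset perfectly separated, 3% against 1% has an SD of √((0.03 × 0.97 + 0.01 × 0.99)/95) = 2.0 points. Much of the noise is simply the small sample.
- *Vital signs depart from the protocol in the same way.* A child under 12 may enter at 60 to 69 bpm while Table 6-1 flags rates below 70, so pre-existing notable values are possible. But the protocol plans no vital-sign shift table, and change from baseline or pre-dose is summarized.

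**Conclusion.** The point holds for hematology and chemistry, except eGFR and low lymphocytes. The SAP does not list a table that the protocol specifies, and without it no listed table separates new from pre-existing notable values.

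The consequence is modest. Ratios between arms are pulled towards 1 and attribution is unclear; there is no systematic bias, and absolute differences shrink only by the factor (1 − b). The size rests on assumed baseline shares of 2% to 10%, equal in both arms and persistent. The true shares will differ by parameter and may be near zero for many. The textual finding needs none of these assumptions. It could be softened only if the table shells turn out to show notable status at baseline.

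**What to change.** In SAP 6.5.4, add for hematology and chemistry a shift table by the notable limits of Table 6-2, from baseline to the most extreme post-baseline value, by treatment group, on the safety set. Because SAP 6.5.2 lets a patient count as both notably low and notably high, tabulate the lowest and highest values separately, with a row for missing baseline. Keep the normal-range shift table. Keep the all-patient incidence table unchanged, so that patients who start beyond a limit and worsen stay visible. If the sponsor prefers not to add the table, the SAP should state and justify the departure from Protocol 9.5.3.

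Optionally, split by baseline status the absolute limits behind this SAP 6.4.3 output: "Incidence of notable vital sign abnormalities based on the notable criteria in Table 6-1". The matching first-dose summary in SAP 6.7.4 can be split by pre-dose status.

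The cost is a sentence or two of SAP text and one table set. All the data are already collected and nothing existing is lost. One limit remains: a patient notable at both times appears as unchanged however much the value worsens, so the listings still have to be read for those patients.
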